12.2.5. Scoring of Laboratory Values

12.2.5.1. Scoring according to normal ranges

All values will be compared to their matching normal ranges. The normal ranges provided by the laboratory will be used for this, as available in the database. Values will be scored as abnormally low (L), normal (N) or abnormally high (H).

A value is classified as abnormally low (L) when the value < lower limit of the normal range. A value is classified as abnormally high (H) when the value > upper limit of the normal range. Values equal to the boundaries are still considered normal (N).

An original value like “<X” where X equals the lower limit of the normal range will be classified as abnormally low (L). An original value like “>X” where X equals the upper limit of the normal range will be classified as abnormally high (H).

A normal range of “<10” will be interpreted as: lower limit = 0; upper limit = 10.

A normal range of “>10” will be interpreted as: lower limit = 10; upper limit = +INF.

Tests without normal ranges will not be scored.

Any already existing low/normal/high flags in the raw database will be ignored. The newly derived flag will be used for the analysis TLFs. Any clinical significance flags will be used in the listings.

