8.8. ACR COMPONENT: SERUM CRP

8.8.1. Parameters

Serum CRP (mg/L) will be analyzed as raw values, change from baseline and percent change from baseline.

Note that if for a specific visit both the regular CRP as well as the high-sensitive CRP are available, the high-sensitive CRP will be used in the analysis tables and figures. The regular CRP will then only be listed.

CRP and hsCRP values will also be categorized according to the lab's normal ranges: normal (value \leq ULN) or high (value $>$ ULN), where ULN = upper limit of the normal range as provided by the central lab. Note that the same ULN (8.999) will be applied to both CRP and hsCRP.

Note that CRP and hsCRP will be excluded from the lab safety analysis.

Note that the percentage change from baseline remains missing if the baseline value itself equals zero.

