12.2.3. Number of Significant Digits

The original results and normal limits will be rounded to present only a relevant number of digits. The Mock TLFs contains a table on the expected number of significant digits per lab test. This rounding will be done prior to any parameter derivation. Note that this table also contains the classification of lab tests into categories.

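### Laboratory scoring: one-sided ranges are read as including their own limit, and results and limits are rounded before scoring, so some results at or just outside a limit can be counted as normal

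*SAP*

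**What the plan says.** SAP section 12.2.5.1 sets the scoring rule for laboratory safety tests:

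- "Any already existing low/normal/high flags in the raw database will be ignored", and "The newly derived flag will be used for the analysis TLFs".
- "A value is classified as abnormally high (H) when the value > upper limit of the normal range". Low is defined the same way at the lower limit, and a value equal to either limit is normal.
- A range supplied as `<10` "will be interpreted as: lower limit = 0; upper limit = 10". A range supplied as `>10` becomes 10 to plus infinity.
- A result reported as `<X` or `>X`, where X is the lower or upper limit respectively, is scored abnormal.

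Section 12.2.3 adds a prior step: "The original results and normal limits will be rounded to present only a relevant number of digits", and "This rounding will be done prior to any parameter derivation". The number of digits per test is in the Mock TLFs, a separate document.

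The flag feeds the baseline abnormality table (14.1.3.3), the shift and treatment-emergent abnormality tables (14.3.2.4 and 14.3.2.5, with their 24-week counterparts) and the abnormalities listing (16.2.11.2). Table 14.3.2.5 is also produced for the Week 12 interim analysis. The flag decides who enters the endocrine tables restricted to a normal baseline.

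**The concern.** There are two separate mechanisms, and both push results towards normal.

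**One-sided ranges.** A laboratory that supplies `<10` is saying that 10 is not normal. Turning the range into 0 to 10 and then treating the limit as normal reverses that call. Because the database flag is ignored, nothing downstream restores it. The section is also inconsistent: it respects the inequality sign when it is attached to a result, but drops it when it is attached to a range.

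**Rounding first.** The low/normal/high flag is a derived parameter, so it is scored on rounded results against rounded limits. Two different numbers can become equal after rounding, and equality is scored normal.

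At stake is the accuracy of descriptive safety counts near the limits of normal, in every arm. Elsewhere the SAP leans the other way. Doubtful post-baseline urinalysis results take the worst case (12.2.6), and QTcF is rounded up before it is categorized (12.3.2).

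**Working it through.** The plan gives no figure to reproduce, so the check applies the rule as written.

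**Inputs from the SAP.** The high, low and boundary rules, the reading of `<10` and the treatment of database flags come from 12.2.5.1. Rounding of results and limits before derivation comes from 12.2.3.

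**Assumptions.** Digits are taken as 0, 1 or 2 decimals, because the digits table is not in the documents. Rounding is half-up, to the same number of decimals for a result and its limits.

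**Step 1: fixed values against a range supplied as `<10`.**

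| Result | Strict `<10` | SAP, unrounded | SAP, 1 decimal | SAP, 0 decimals |
|---|---|---|---|---|
| 9.9 | N | N | N | N |
| 10 | H | N | N | N |
| 10.04 | H | H | N | N |
| 10.4 | H | H | H | N |
| 10.5 | H | H | H | H |

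The row for 10 is the one-sided-range effect and does not depend on rounding. The rows for 10.04 and 10.4 are the rounding effect.

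**Step 2: direction of the rounding effect.** Let R be rounding to k decimals, v the result and U the upper limit. R never reverses an order.

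- If v ≤ U, then R(v) ≤ R(U), so a result that is not high cannot become high.
- If v > U, then R(v) ≥ R(U). If the two are equal, the result is scored normal.
- Equality requires v and U to lie in the same rounding interval, so the lost excess v − U is less than one rounding unit.

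The same argument holds at the lower limit. A simulation of 200,000 result/limit sets per setting agrees:

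| Decimals | H to N | L to N | N to H or L | Largest excess over upper limit lost |
|---|---|---|---|---|
| 2 | 59 | 67 | 0 | 0.009 |
| 1 | 636 | 691 | 0 | 0.098 |
| 0 | 6,731 | 6,779 | 0 | 0.985 |

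These counts show direction and bound; the simulated values are arbitrary. One worked case: with an upper limit of 10.6 and a result of 11.4, both become 11 at 0 decimals, so H becomes N.

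**Step 3: illustrative size.** Assume lognormal results with median 10 and log-SD 0.45, and a limit of 20. All three are assumptions and none is tied to a study test. Write S(x) = 1 − Φ(ln(x/10)/0.45), and let h be half a rounding unit (0.5, 0.05 or 0.005).

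- Range `<20`, results recorded to k decimals: abnormal is S(20 − h), flagged is S(20 + h), share lost is 1 − S(20 + h)/S(20 − h).
- Upper limit 20, finer results rounded to k decimals before scoring: abnormal is S(20), flagged is S(20 + h), share lost is 1 − S(20 + h)/S(20).

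| Decimals | S(20 − h) | S(20) | S(20 + h) | Lost, `<20` | Lost, rounding |
|---|---|---|---|---|---|
| 0 | 0.0689 | 0.0617 | 0.0553 | 19.7% | 10.4% |
| 1 | 0.0624 | 0.0617 | 0.0611 | 2.2% | 1.1% |
| 2 | 0.0618 | 0.0617 | 0.0617 | 0.2% | 0.1% |

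**Step 4: treatment-emergent counts.** Table 14.3.2.5 calls a post-baseline abnormality treatment-emergent if it differs from baseline, and baseline is scored by the same rule. A post-baseline result moved from H to N removes an event. A baseline result moved from H to N makes a later H newly treatment-emergent and adds one. The net sign is not determined.

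**The case against.** The strongest case against is that neither mechanism is shown to act in this trial. If the Mock TLF digits match the laboratory's reporting precision, rounding changes nothing. The SAP offers `<10` and `>10` as parsing examples, and no safety test is shown to have such a range. For two-sided ranges, calling a value on the limit normal is an ordinary convention. All of this stands, and it is why the point is conditional in size. It does not defend the rules, which misclassify whenever the conditions are met.

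There are real mitigations. Results censored at the limit are scored abnormal. The listings carry the actual data with each test's normal range, and clinically significant abnormalities are listed separately. Larger excursions are still flagged. The tables have no p-values, and the rule is the same in every arm.

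A reader might draw three stronger conclusions that the documents do not support:

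- **CRP shows that the team knew of the problem.** Section 8.8.1 says "Note that the same ULN (8.999) will be applied to both CRP and hsCRP", which could look like a deliberate way round the boundary. The same section says the upper limit is provided by the central laboratory, so it shows no choice by the analysis team. CRP is also excluded from the laboratory safety analysis.
- **Treatment-emergent abnormalities are under-reported.** Step 4 shows that they can move either way.
- **Ignoring database flags is itself an error.** Re-deriving every flag by one algorithm from the laboratory's own ranges is a consistent approach. It matters here only because it removes the one thing that could have corrected the score.

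**Conclusion.** The point holds as a minor, conditional defect. As written, section 12.2.5.1 scores a result equal to X as normal when the supplied range is `<X` or `>X`. Section 12.2.3 makes ties out of results less than one rounding unit outside either limit whenever display digits are coarser than laboratory precision. Abnormality counts per time point and the abnormalities listing can be slightly too low, and the direction for treatment-emergent counts is open. CTCAE grades whose boundary is the upper or lower limit of normal inherit the rounding.

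The size cannot be given from the documents. It is zero if the digits match laboratory precision and no one-sided range applies. The 10–20% at 0 decimals is the coarsest illustrative case under invented distribution values; it falls to 1–2% at 1 decimal and 0.1–0.2% at 2 decimals. A reader might take the upper figure as an estimate for this trial, but nothing in the documents ties it to a study test. No efficacy result is affected.

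**What to change.** Amend two places in the SAP.

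- **12.2.3:** state that low/normal/high flags, and CTCAE grades that use the upper or lower limit of normal, are derived from results and limits at the laboratory's reported precision, and that rounding applies to display only.
- **12.2.5.1:** state that where a range is supplied as `<X` or `>X`, a result equal to X is abnormal (high or low respectively). This brings ranges into line with the existing rule for censored results.

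Keep the single re-derived flag; mixing in the laboratory's own flags would create two scoring systems. The cost is about two sentences and a small programming change. The downside is that a few more borderline abnormalities will be reported.

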12.2.5.2. CTCAE V3.0 gradings for biochemistry tests

CTCAE version 3.0 classification is only for the below tests. For other tests, only the classification according to normal ranges will be done.

Lab test	Grade 0	Grade 1	Grade 2	Grade 3	Grade 4
Albumin (g/L)	≥ LLN	[30,LLN[[20,30[<20	(NAP)
ALT, AST, alkaline phosphatase and γGT	≤ ULN]1.0,2.5] x ULN]2.5,5.0] x ULN]5.0,20.0] x ULN	> 20.0 x ULN
Amylase and lipase	≤ ULN]1.0,1.5] x ULN]1.5,2.0] x ULN]2.0,5.0] x ULN	> 5.0 x ULN
Total bilirubin	≤ ULN]1.0,1.5] x ULN]1.5,3.0] x ULN]3.0,10.0] x ULN	> 10.0 x ULN
Calcium low (mmol/L)	≥ LLN	[2.00,LLN[[1.75,2.00[[1.50,1.75[<1.50
Calcium high (mmol/L)	≤ ULN]ULN,2.9]]2.9,3.1]]3.1,3.4]	>3.4
Total cholesterol (mmol/L)	≤ ULN]ULN,7.75]]7.75,10.34]]10.34,12.92]	>12.92
Creatinine	≤ ULN]1.0,1.5] x ULN]1.5,3.0] x ULN]3.0,6.0] x ULN	> 6.0 x ULN
Glucose low (mmol/L)	≥ LLN	[3.0,LLN[[2.2,3.0[[1.7,2.2[<1.7
Glucose high (mmol/L)	≤ ULN]ULN,8.9]]8.9,13.9]]13.9,27.8]	>27.8
Phosphate (mmol/L)	≥ LLN	[0.8,LLN[[0.6,0.8[[0.3,0.6[<0.3
Potassium low (mmol/L)	≥ LLN	[3.0,LLN[(NAP)	[2.5,3.0[<2.5
Potassium high (mmol/L)	≤ ULN]ULN,5.5]]5.5,6.0]]6.0,7.0]	>7.0
Sodium low (mmol/L)	≥ LLN	[130,LLN[(NAP)	[120,130[<120
Sodium high (mmol/L)	≤ ULN]ULN,150]]150,155]]155,160]	>160
Triglycerides	≤ ULN]1.0,2.5] x ULN]2.5,5.0] x ULN]5.0,10.0] x ULN	> 10.0 x ULN

Note:

– LLN = lower normal limit

- ULN = upper normal limit
- (NAP) = grade does not exist.

12.2.5.3. CTCAE v3.0 gradings for hematology tests

CTCAE version 3.0 classification is only for the below tests. For other tests, only the classification according to normal ranges will be done.

Lab test	Grade 0	Grade 1	Grade 2	Grade 3	Grade 4
Hemoglobin (g/L)	≥ LLN	[100,LLN[[80,100[[65,80[< 65
WBC (giga/L)	≥ LLN	[3.0,LLN[[2.0,3.0[[1.0,2.0[<1.0
Lymphocytes (giga/L)	≥ LLN	[0.8,LLN[[0.5,0.8[[0.2,0.5[< 0.2
Neutrophils (giga/L)	≥ LLN	[1.5,LLN[[1.0,1.5[[0.5,1.0[< 0.5
Platelet count (giga/L)	≥ LLN	[75,LLN[[50,75[[25,50[< 25
INR and partial thromboplastin time	≤ ULN]1.0,1.5] x ULN]1.5,2.0] x ULN	>2.0 x ULN	(NAP)

Note:

- LLN = lower normal limit
- ULN = upper normal limit
- (NAP) = grade does not exist.

12.2.5.4. ATP III classifications

Lab test	Categories				
LDL (mg/dL)	< 100	[100,130[[130,160[[160,190[≥ 190
HDL (mg/dL)	< 40	[40,60[≥ 60		
Total cholesterol (mg/dL)	< 200	[200,240[≥ 240		
Triglycerides (mg/dL)	< 150	[150,200[[200,500[≥ 500	

12.2.6. Handling of Urinalysis Results

Urinalysis tests for which a normal range is available will also be categorized as L, N, or H. If there is doubt on whether the result is within normal range or not, the worst-case will be taken. E.g., when the test result equals “4 to 6” and the normal range is 0-5, then the test result will be classified as abnormally high (H) if it is a post-baseline visit, and will be classified as normal (N) if it is a screening or baseline visit. The original urinalysis test result will not be used for the tables, but will only be listed.

Urinalysis tests for which no normal range is available will be tabulated separately as categorical data.

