Shift table per lab test category (hematology, biochemistry, endocrine, urinalysis), lab test, treatment group and time point. The table will present the shift in abnormality (L/N/...) at worst-case and last on-treatment (other time points: not needed) versus the baseline abnormality (L/N/H). Tests without normal ranges will not be presented in this table.

Population: safety.

Table 14.3.2.5: Laboratory data up to Week 12: Treatment-emergent lab abnormalities per time point

Frequency table of the treatment-emergent lab abnormalities per lab test category (hematology, biochemistry, endocrine, urinalysis), lab test, treatment group and time point (including the worst-case). A post-baseline abnormality is considered treatment-emergent if it differs from the baseline result. Tests without normal ranges will not be presented in this table.

Population: safety.

Table to be created for the Week 12 interim analysis as well.

Table 14.3.2.6: Laboratory data up to Week 12: Frequency table of the CTCAE toxicity grades per time point

Frequency table (with cumulative percentages) per lab test category (hematology, biochemistry, endocrine, urinalysis), lab test, treatment group and time point.

Table for selected tests only.

Population: safety.

Table to be created for the Week 12 interim analysis as well.

Table 14.3.2.7: Laboratory data up to Week 12: Shift table of the CTCAE toxicity grades per time point

Shift table per lab test category (hematology, biochemistry, endocrine, urinalysis), lab test, treatment group and time point. The table will present the shift in CTCAE tox grade (0/1/2/3/4) at worst-case and last on-treatment (other time points: not needed) versus the baseline grade (0/1/2/3/4).

Table for selected tests only.

Population: safety.

Table 14.3.2.8: Laboratory data up to Week 12: Treatment-emergent CTCAE toxicity grades per time point

Frequency table of the treatment-emergent lab CTCAE tox grades per lab test category (hematology, biochemistry), lab test, treatment group and time point (including worst-case). A

post-baseline grade is considered treatment-emergent if it is higher than the baseline tox grade.

Table for selected tests only.

Population: safety.

Table to be created for the Week 12 interim analysis as well.

Table 14.3.2.9: Laboratory data up to Week 12: Frequency table of the ATP III classes per time point

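### A urinalysis range result that straddles a normal limit is scored normal at baseline and abnormal afterwards, so an identical result is counted as a treatment-emergent abnormality

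*SAP*

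**What the plan says.** SAP 12.2.6 covers urinalysis tests that have a normal range. It starts from a general principle: "If there is doubt on whether the result is within normal range or not, the worst-case will be taken". Its example is a result of 4 to 6 against a range of 0–5, which is scored "abnormally high (H) if it is a post-baseline visit, and will be classified as normal (N) if it is a screening or baseline visit". The section then adds: "The original urinalysis test result will not be used for the tables, but will only be listed".

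SAP 12.2.9 defines the tables that use these categories:

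- Table 14.3.2.4 (shift): "The table will present the shift in abnormality (L/N/...) at worst-case and last on-treatment", set against the baseline category, with urinalysis among the test categories.
- Table 14.3.2.5 (treatment-emergent) also names urinalysis. Its rule is: "A post-baseline abnormality is considered treatment-emergent if it differs from the baseline result". This table is also produced for the Week 12 interim analysis.

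SAP 12.2.11 repeats both for the whole study as Tables 14.3.2.17 and 14.3.2.18. Neither 12.2.6 nor 12.2.9 exempts a result that has not changed.

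**The concern.** A treatment-emergent table should count subjects whose finding appeared or changed after dosing started. Here the category depends on the visit as well as on the measurement. Because the raw result is kept out of the tables, the comparison with baseline can only be a comparison of categories. A subject with the same entry at every visit then appears as a new abnormality.

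The SAP's other laboratory conventions do not behave this way. The scoring rules in 12.2.5.1 for boundary values and for results given as below or above a limit, and the detection-limit rule in 4.3.1, treat a given value alike at every visit.

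At stake are the absolute treatment-emergent counts for urinalysis and the normal-to-abnormal shifts. Up to Week 12 a placebo column shows the same inflation. The whole-study tables use the five treatment sequences of SAP 2.1.2, none of which stays on placebo, so period 2 has no concurrent placebo rate to judge the counts against.

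**Working it through.** **Inputs.** The scoring rule and example come from SAP 12.2.6. The treatment-emergent definition comes from SAP 12.2.9 (Table 14.3.2.5). SAP 12.2.8.1 lets a single post-dose value above range make the worst case high. There are five scheduled post-baseline visits up to Week 12 (Weeks 1, 2, 4, 8 and 12), and 70 subjects per arm (Protocol 8.5.4). The share s of straddling results is not in the documents. It is assumed at 2%, 5% and 10%.

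**Step 1: apply the rules to cases (range 0–5).** TE means abnormal after baseline and different from the baseline category.

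| Baseline → later | SAP rule | Straddling always N | Straddling always H | SAP rule, identical result keeps baseline category |
|---|---|---|---|---|
| 4–6 → 4–6 | N→H, TE | N→N, no | H→H, no | N→N, no |
| 0–2 → 4–6 | N→H, TE | N→N, no | N→H, TE | N→H, TE |
| 4–6 → 6–8 | N→H, TE | N→H, TE | H→H, no | N→H, TE |
| 4–6 → 0–2 | N→N, no | N→N, no | H→N, no | N→N, no |
| 6–8 → 4–6 | H→H, no | H→N, no | H→H, no | H→H, no |

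The first row is the fault: the recorded result is identical and the SAP rule counts it. Rows two and three are recorded changes, and the last column still counts both.

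**Step 2: size of the excess.** The visit-dependent scoring creates an extra case only when the baseline itself straddles and a later result straddles again.

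- Fully persistent results: a subject who straddles at baseline straddles throughout, so the excess is s.
- Independent visits: the excess is s × [1 − (1 − s)^5].

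| s (assumed) | 1 − (1 − s)^5 | Excess, independent | Excess, persistent | False cases per 70 |
|---|---|---|---|---|
| 2% | 0.096 | 0.02 × 0.096 = 0.2% | 2% | 0.1–1.4 |
| 5% | 0.226 | 0.05 × 0.226 = 1.1% | 5% | 0.8–3.5 |
| 10% | 0.410 | 0.10 × 0.410 = 4.1% | 10% | 2.9–7.0 |

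These figures are per test. More visits, including the unscheduled values that SAP 12.2.8 admits to the worst case, raise the independent figure, but s remains the ceiling.

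**Step 3: effect on a between-arm contrast.** If a fraction f of every arm is falsely counted, independently of true events, an observed rate is p + f(1 − p). The difference between arms becomes (1 − f)(p₁ − p₀). With f at most s, a true risk difference shrinks by at most 2%, 5% or 10% of its value under the three assumptions.

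**The case against.** The strongest defence is that the rule is deliberate and disclosed. The SAP resolves other safety doubts towards the worse reading: missing relatedness counts as related (12.1.2), and incomplete adverse event dates are allocated on a worst-case basis (12.1.1). Over-counting in every arm favours no arm. The tables carry no p-values (12.2.9), and raw urinalysis results remain visible by subject and time point in Listing 16.2.11.4. All of this stands and limits the weight of the point. It does not remove the fault. In those other rules the missing fact is unknown. Here the position relative to the limit is unknown, but the two recorded results are known to be the same.

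A second defence is that straddling results may be rare. The visit procedures in Protocol 8.6 include microscopy, a plausible source of range results, but the itemised urinalysis panel in Protocol 8.7.1.4.2 lists no microscopy count. SAP 12.2.1 sends tests outside the planned panels to listings only, and 12.2.6 tabulates tests without a normal range separately. This also stands: the SAP foresees range results, but nothing shows how often they occur.

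A reader might infer a much larger effect by taking 1 − (1 − s)^5 as the false rate, which gives 9.6%, 22.6% and 41.0% for the three assumed shares. The documents do not support that. The expression counts every subject with any straddling result after baseline, including those who moved from clearly normal to straddling. That is a recorded change, and scoring straddling results as abnormal at every visit would count it too. Under independence it overstates the excess by a factor of 1/s: 50, 20 and 10.

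A reader might also infer that straddling results should simply be scored by their upper end at every visit. That would hide a move from straddling to clearly high (third row of the first table), would score a result straddling a lower limit as normal, and would add baseline abnormalities to Table 14.1.3.3.

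**Conclusion.** The point holds in a narrow form. Under SAP 12.2.6 and 12.2.9 together, an identical straddling urinalysis result at baseline and later is counted as treatment-emergent and as a shift, and nothing in the plan prevents it. It reaches only urinalysis tests that have a normal range and are reported as a range crossing a limit.

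The excess per test by Week 12 is at most the share of subjects who straddle at baseline, and much less if straddling does not persist. The range given rests on an assumed s and on the two extremes of persistence. The effect is inflated absolute counts in descriptive tables for all arms, including a table supplied to the interim analysis that supports preliminary dose selection (SAP 6.2). Any dilution of a between-arm difference is slight. It is worth correcting because the correction is small, not because it threatens a conclusion of the trial.

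**What to change.** Keep the worst-case scoring in SAP 12.2.6 and add one sentence: *a post-baseline urinalysis result identical to the raw baseline result is given the baseline category and is not counted as treatment-emergent or as a shift.*

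This removes the false cases from unchanged results, still counts a move from straddling to clearly abnormal, works for lower as well as upper limits, and leaves the baseline table as it is.

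The cost is one derivation step comparing raw results, and a slightly smaller treatment-emergent count. Two limits should be noted. A later result that straddles but is recorded as a different range will still be counted. And final-analysis counts up to Week 12 may then differ from those in the interim version of Table 14.3.2.5, so the change belongs in the SAP 6.3 record of changes.
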